3.3.1 Primary Endpoint

The primary endpoints will be quantitative and qualitative measures of FES uptake, and measures of change in FES uptake between pre-therapy and post-therapy scans

3.3.2 Secondary Endpoint

Progression-free survival.

3.4 Estimated Accrual

We anticipate that we will enroll up to 20 patients in this pilot study.

4.0 SAFETY CONSIDERATIONS

4.1 Stopping Rules

Participant involvement will be concluded if any AEs possibly related to the IP occur. The principal investigator will exercise their discretion in determining which AEs may be related to the IP. This excludes mild pain, bruising, or controllable bleeding at the injection site, which is a common and expected risk for IV imaging products.

5.0 BRIEF DESCRIPTION OF MANUFACTURING PROCESS FOR F-18 FES

This product is manufactured under IND# 101203. The chemical precursor for [18F]FES is provided in house or by Advanced Biological Compounds in single-use, 2 mg vials that are delivered to the custody of [name], the lead radiochemist for this project. They are stored in a controlled temperature freezer in a locked and secure room and they are inventoried with a chain of custody maintained from the time of receipt. Each radiosynthesis is assessed by a radiochemist for quality. The quality control tests that must be passed prior to release of the product [18F]FES for injection include the pH, radioactive purity, radiochemical purity, specific activity, sterilizing filter integrity, tests for Kryptofix, acetonitrile, endotoxins and particulates. Acceptance criteria are detailed in the CMC document. The [18F]FES dose is drawn up into a syringe, assayed for mCi at time of injection, labeled and administered to the research subject.

6.0 SUBJECT ELIGIBILITY

6.1 Inclusion Criteria

- Adult, non-pregnant patients with biopsy-proven or clinically obvious primary, recurrent or metastatic breast cancer
- Breast cancer from ER+ primary that is seen on other imaging tests. Tumor ER expression must have been confirmed by immunohistochemistry of primary tumor or recurrent disease.
- At least one site of disease 1.5 cm or greater is needed to meet the spatial resolution limits of PET imaging.
- Patients must have been off tamoxifen or other estrogen receptor blocking agents for at least 6 weeks and off chemotherapy for 3 weeks for the initial baseline FES.
- Patients must be selected for an endocrine targeted therapy regimen for treatment of their breast cancer by the referring oncologist. Selected treatments may be part of experimental treatment protocols for which the patient would be separately consented.
- Patients must be willing to undergo serial imaging procedures.
- Patients must agree to allow access to clinical records regarding response to treatment and long term follow up.
- Ability to understand and the willingness to sign a written informed consent document.

6.2 Exclusion Criteria

- An inability to lie still for the tests
- Individuals weighing more than 300 lb. (this is the weight limit of the scanner table)
- Pregnant or lactating. Women of childbearing potential with either a positive or no pregnancy test at baseline are excluded.
- Any other life-threatening illness (e.g. serious, uncontrolled concurrent infection or clinically significant cardiac disease – congestive heart failure, symptomatic coronary artery disease, cardiac arrhythmia not well controlled with medication).
- Use of tamoxifen, faslodex, DES or any other ER blocking agent < 6 weeks or chemotherapy < 3 weeks prior to imaging scan.
- Unwillingness or inability to give informed consent.
- Uncontrolled diabetes mellitus (fasting glucose > 200 mg/dL)
- Adult patients who require monitored anesthesia for PET scanning.

7.0 SUBJECT REGISTRATION

Subjects will be registered by the Fred Hutch/UW Study Coordinator and entered into the Clinical Trials Management System (CTMS). A complete, signed, study consent and HIPAA consent are required for registration.

8.0 TREATMENT PLAN

Treatment will be administered on an outpatient basis. Reported adverse events are described in section 13.0 and potential risks are described in section 2.6. There will be no dose modifications for FES administration. No investigational or commercial agents or therapies will be administered in this protocol with the intent to treat the patient's malignancy.

8.1 Treatment Plan Overview

Figure 6.1 Outline (Schema) of the [18F]FES Study Protocol. a) FDG PET is not required for primary breast cancer patients unless required for localization or requested by treating physician. b) Where available and medically appropriate, a clinical or research biopsy that involved sampling of a relevant lesion within 6 months prior to the enrollment may be utilized in place of the baseline optional biopsy. c) Repeat FDG PET may be omitted in patients on SERD therapies.

Initial visits prior to [18F]FES PET: Patients who are identified as potential candidates for the [18F]FES PET study will be approached to explain the nature of the study and to obtain their written informed consent to be enrolled in the protocol. Heart rate and blood pressure will be recorded at the time of clinic visit where study is considered or at the time of consent. The patient will have a clinical FDG PET/CT scan if a recent FDG scan has not already been obtained. The FDG PET/CT scan should be obtained close to the time of FES PET/CT, typically within 14 days of the [18F]FES PET/CT scan. An additional FDG PET/CT scan may be done as a research scan if the patient has undergone a recent PET scan at an outside institution or if they are unable to obtain a clinical PET scan as part of their clinical care. The research FDG PET/CT scan in this instance will be identical in procedure to a clinical FDG scan. The following additional patient data will be obtained: histological diagnosis, age at radiologic diagnosis, weight, gender, ECOG score and other treatment modalities used. Correlative radiology including CT, MRI, or bone scan, and laboratory tests measuring renal, blood and liver function will also be collected, for values within 30 days of the FES PET/CT scan. For patients referred from outside the UW health system, patient records, and biopsy material and imaging as necessary, will be reviewed to determine eligibility for the study. Patients without a clinical evaluation in the last 30 days are unexpected; in these instances a clinical evaluation will be completed.

Day of [18F]FES PET/CT Scan: After the FES injection and rest period (section 6.6.1), the patient will be positioned supine in the PET/CT scanner. A low dose CT scan (60 mA) will provide attenuation correction data using non-contrast CT. The PET image acquisition sequence will be the same as that used for clinical FDG scans. This consists of a torso survey series of five-minute images acquired over 15 cm survey fields of view (FOVs) extending from the base of the skull to the mid thigh (5 to 7 FOVs in total). The images will be corrected for radioactive decay of the tracer and normalized to the injected dose and body weight. This results in regional standardized uptake values (SUVs) whole-body image sets.

Prior to injection, a whole blood sample may be taken for determination of albumin, estradiol and testosterone levels, heart rate and blood pressure will be recorded. A known quantity of nonradioactive FES will be added to plasma (from blood collected prior to injection) to determine binding to sex steroid binding protein (SBP). For patients in whom a second venous access line is feasible and has been placed, venous blood samples may be collected at 5, 20 and 60 minutes after injection of the [18F]FES for metabolite analysis in selected patients. Heart rate and blood pressure will be measured after the FES injection.

After the [18F]FES PET Scan: A follow up phone call will be made by study staff within 24 hours after the FES PET scan to ask about any signs of adverse effects. Patients will typically start the selected hormone targeted therapy within 30 days of the FES PET scan. Patients who have started aromatase inhibitors prior to [18F]FES PET will be permitted to enter the study, if an additional endocrine targeted treatment is planned.

In patients who consent to optional biopsies, a baseline tumor sample will be obtained after completion of the baseline PET imaging but prior to starting the selected endocrine targeted therapy. Where available and medically appropriate, a clinical or research biopsy that involved sampling of a relevant lesion within 6 months prior to the enrollment may be utilized in place of the baseline optional biopsy.

In some patients undergoing biopsies, a whole blood sample will be collected prior to starting the therapy, to allow correlation of steroid hormone levels in serum and biopsy tissue.

Repeat FES PET scan and FDG PET scan: Patients will undergo a second FES PET and FDG PET scan after starting endocrine targeted therapy to assess the effect of therapy on ER expression and estradiol binding to the receptor. Exact timing of the second FES and FDG scans, will depend upon the endocrine targeted regimen and dosing, but typically will be 1 – 12 weeks after starting therapy.

The repeat FDG PET may be omitted in patients on SERD therapies, where repeat FES PET is used primarily to evaluate residual ER availability rather than tumor response. This will be determined by requirements of the co-enrolling companion therapeutic protocol.

Optional Biopsy: In patients who consent to optional biopsies, an early response tumor sample will be obtained 1-12 weeks after starting the selected therapy. This biopsy should take place after completion of the repeat PET imaging and should target the same tumor site as the baseline biopsy. A whole blood sample may be drawn for correlation of steroid hormone levels in serum and biopsy tissue.

Week 1 to 20 years after [18F]FES PET Scan: Clinical follow-up will continue for up to 20 years, time of progression and date of death will be recorded. For some patients, especially those receiving two endocrine-directed treatments, a third FES PET scan and additional research FDG PET scan may also be obtained 1-12 weeks after the second FES PET scan. For each patient, a maximum of 3 FES PET and 3 FDG PET scans would be done.

A study calendar is included in Appendix A.

8.1 Administration of IP (FES PET)

FES will be administered in the PET imaging suite at the University of Washington Medical Center or at the Seattle Cancer Care Alliance (SCCA). The [18F]FES for injection will be prepared as described in section 6.6.2, Study Procedures and Schedule of Events. Upon arrival, the patient will have an opportunity to have questions answered regarding the procedure. The patient will have an intravenous line placed prior to [18F]FES administration. A dose of nominally 220 MBq (6 mCi with a range of 110 to 220 MBq = 3 to 6 mCi) of [18F]FES will be administered intravenously by a physician. The injection will be infused over approximately 2 minutes and followed by a saline flush. The infusion and imaging procedure will be terminated in any patient who exhibits anaphylaxis, physical signs of significant hypotension, significant dyspnea or chest pain. We do not expect to observe any of these effects as no events have been reported in more than 300 scans performed with this compound at our institution to this date. The patient will then be allowed to rest comfortably in a prep room prior to being positioned in the PET scanner to commence the image acquisition at 60 +/- 10 minutes post FES injection.

Heart rate and blood pressure will be recorded pre- and post-FES dosing, and will continue to be monitored after injection until baseline is achieved.

Patients will be monitored for adverse events, potentially related to the administration of [18F]FES, from the time of the initial injection to 10 hours post injection. Any adverse events will be recorded and reported according to FDA requirements (see section 13.0, Adverse Events).

8.2 Administration of FDG PET

In most cases, a standard clinical diagnostic FDG PET or PET/CT scan will be obtained prior to the [18F]FES PET scan. The FDG PET or PET/CT scan serves to help identify active sites of breast cancer and is used to help determine sites on the FES PET scan where estradiol binding would be expected. At least one site of measurable disease outside of the liver, where quantification of FES uptake can be difficult because of normal biodistribution, must be evident on the FDG PET scan and CT or MRI. FDG PET imaging will be completed close to the time of the FES PET scan. In select cases where the baseline FDG PET is being repeated at our institution for the purposes of this study it may be completed after the FES PET. The FDG PET will be a clinical 5 axial field-of-view (AFOV) scan from skull base to mid-thigh. Maximum SUV of identified lesions will be calculated and recorded as per standard clinical procedure.

For FDG PET or PET/CT, all patients will fast for at least 4 hours before PET scanning. All patients must have a medical history negative for diabetes and/or a pre-scan serum glucose level less than 200 mg/dL. A dose of 260-370 MBq (7-10 mCi) of FDG will be injected into a peripheral intravenous or central venous catheter. Patients will rest comfortably in a supine position prior to scanning. Imaging will be performed with a commercially made PET/CT scanner operating in the high sensitivity mode. Imaging will consist of a torso survey covering five adjacent 15-cm axial fields of view (FOVs). For the PET/CT device, a low dose CT scan beginning at approximately 60 minutes after FDG injection provides attenuation data for attenuation correction using a non-contrast CT. Emission data will be collected for all five axial FOVs, typically five minutes per FOV.

Emission data will be reconstructed according to standard protocols. Images will be corrected for radioactive decay of the tracer and normalized to the injected dose and body weight, which results in regional standardized uptake values (SUVs): as defined in section 6.10.3.

We emphasize that the baseline FDG PET or PET/CT is part of standard clinical care of metastatic and recurrent breast cancer and will be performed as part of routine clinical care in the vast majority of patients participating in the study. Methodology for FDG PET is included in this section for reference purposes. In some cases, FDG PET or PET/CT will have already been performed at an outside center at the time of enrollment. On rare occasions when patients have been referred to the study with a recent FDG PET scan already completed at an outside site that is unavailable or of insufficient detail for our study, or the patient is unable to obtain a PET scan as part of standard clinical management, we will repeat the FDG PET at the University of Washington as a research scan, however, the imaging procedure will not vary from that of a standard clinical scan.

Patients will undergo a second (and potentially a third in a subset of patients) FDG PET following the same imaging procedure as part of the research study. This second scan will be performed at a time point stipulated by the treatment regimen and may vary from 1 to 12 weeks post therapy start.

8.3 Concomitant Medication and Supportive Care Guidelines

Because interaction of < 5 µg of [18F]FES with other concomitantly administered drugs through the cytochrome P450 system or other pathways is extremely unlikely, this section is not applicable. The infusion and imaging procedure will be terminated in any patient who exhibits adverse reactions as described in section 4.

8.4 Duration of Therapy

As this is an observational study, the results of [18F]FES PETs and repeat FDG PETs are not used to direct therapy, and the duration of therapy is determined on the basis of clinical grounds by the referring physician, and is not influenced by the FES study.

8.5 Duration of Follow-Up

Patients will be followed up to 20 years after [18F]FES PET. Patients removed from study for unacceptable adverse events will be followed until resolution or stabilization of the adverse event.

8.6 Dosing Delays/Dose Modifications

As this is a trial of a diagnostic imaging agent to be administered before endocrine therapy, dosing delays and dose modifications are not relevant to this protocol. FES administration will be stopped if there are any signs of toxicity.

8.7 End of Treatment (EOT) Visit Schedule and Procedures

EOT visits will not be used on this trial.

9.0 SUBJECT EVALUATION

9.1 On-Study Clinical Evaluations

To establish a baseline, this study plans to pull data from recent clinic visits for patients matching the eligibility criteria, if the visits occurred within the last 30 days. If one is not available, clinical evaluations will take place proceeding both the first and second FES scans (and the third, if applicable). These visits should occur as close to the FES scan as possible but must be within 30 days (+/-) of the FES scan. The following tests and procedures would be completed, although not all tests may be done at each visit;

- Physical Examination

- Vitals
- Labs:
 - Hematology: CBC, differential, platelets
 - Serum Chemistries: including calcium, magnesium, SGOT, SGPT, alkaline phosphatase, LDH, total bilirubin, BUN, creatinine, electrolytes, and glucose

Prior to FES administration, the following are completed:

- A whole blood sample may be taken (10mL) (optional)
 - A known quantity of nonradioactive FES will be added to plasma (from blood collected prior to injection) to determine binding to sex steroid binding protein (SBP).
- Heart rate and blood pressure

Following FES Administration, the following are completed:

- For patients able to have a second venous access, venous blood samples may be collected at 5, 20, and 60 minutes after collection.
- Heart rate and blood pressure

10.0 TOXICITY MONITORING

Both acute and chronic toxicities are recorded and reported to the Sponsor, or its designee, and will be reviewed by the independent DMC at scheduled meetings. Monitoring for acute toxicity takes place during and immediately following IP administration for a period of 2 hours at the study site. Subjects are observed for the development of an immediate localized allergic reaction or anaphylactic reaction during this time. Chronic toxicity is evaluated describe here. Describe acceptable or unacceptable toxicity treatments here.

11.0 SUBJECT DISCONTINUATION OF ACTIVE TREATMENT

Subjects may be removed from this study at any time at their discretion. Subjects may also be removed from this protocol if they develop any untoward side effects from the imaging product.

If a subject withdraws consent to participate in the study or aspects of the study, attempts should be made to obtain permission to record survival data up to the protocol-described end of the subject follow-up period. Survival data are important to the integrity of the final study analysis. Documentation in the medical record should state that the subject is withdrawing from the study and what, if any, selected data the subject will permit the investigator to obtain.

An explanation for discontinuing treatment is recorded for each subject discontinuing treatment in the study source. The Sponsor must be notified immediately if a subject discontinues treatment. All subjects, irrespective of treatment status, will continue to be followed for survival. Treatment in this study must be discontinued for any of the following reasons:

- if the Sponsor decides to stop the study;
- at Investigator's discretion;
- at the subject's request;
- if the subject enrolls in a trial of another investigational agent;
- Any adverse event possibly related to the IP, excluding mild pain, bruising, or controllable bleeding at the injection site
- pregnancy

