13.4 Monitoring and Recording Adverse Events

All AEs will be assessed by the investigator or qualified designee and recorded in the source documentation. The investigator should attempt to establish a diagnosis of the event on the basis of signs, symptoms and/or other clinical information. In such cases, the diagnosis should be documented as the adverse event and/or serious adverse event and not described as the individual signs or symptoms. The following information should be recorded:

- Description of the adverse event using concise medical terminology
- Description as to whether or not the adverse event is serious, noting all criteria that apply
- The start date (date of adverse event onset)
- The stop date (date of adverse event resolution)
- The severity (grade) of the adverse event
- A description of the potential relatedness of the adverse event to study drug, a study procedure, or other causality
- The action taken due to the adverse event
- The outcome of the adverse event

Because adverse events are not expected for this IP, and have not been seen in our experience with FES, patients with AEs possibly related to the IP will be discontinued. The principal investigator will exercise their discretion in determining the attribution of AEs.

Patients who discontinue the study will be asked if follow-up via telephone is acceptable. If they agree to receive communication from us, we will follow-up with them 30 days following administration of the IP. If any unexpected risks are discovered which may affect patients more than 30 days following administration, all previous participants will be informed.

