Measurement of these tumor-associated indices may enhance the predictive value of PET FES, provide information to better understand mechanisms of resistance to endocrine therapy, and eventually determine which patients are likely to appreciate clinical benefit as a result of endocrine therapy, even in the absence of an objective response.

Time to progression (Progression-free survival): Time to progression (and progression-free survival) will be measured as the time from the start of endocrine therapy to the time the patient is first recorded as having disease progression. If a patient never progresses while being followed, the patient will be censored at the time he/she terminates follow-up or by date of disease progression or death.

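### After discontinuation Section 11.0 names survival as the only outcome to follow, and the PFS censoring date in Section 14.0 is not tied to the last progression assessment, so unobserved time can count as progression-free

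*Combined protocol and SAP*

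**What the plan says.** The secondary endpoint in Section 3.3.2 is one line: "Progression-free survival". Overall survival is not named there.

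Section 11.0 covers patients who stop. It says "All subjects, irrespective of treatment status, will continue to be followed for survival". For a patient who withdraws consent, "attempts should be made to obtain permission to record survival data up to the protocol-described end of the subject follow-up period", and the chart should note any other data the patient allows. Progression is not mentioned in that section.

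Section 14.0 measures time to progression, which it equates with PFS, from the start of endocrine therapy to the first recorded progression. If none is recorded during follow-up, "the patient will be censored at the time he/she terminates follow-up or by date of disease progression or death". No rule refers to the last disease assessment.

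Progression follow-up appears elsewhere, without an exception for patients who stop. Section 8.1 (Treatment Plan Overview) records progression and death for up to 20 years, Section 17.0 says patients will be followed for progression, and Section 14.0 says they may be. Section 6.1 makes record access an entry condition: "Patients must agree to allow access to clinical records regarding response to treatment and long term follow up".

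Three further sections bear on a patient who stops:
- Section 4.1: "Participant involvement will be concluded if any AEs possibly related to the IP occur", with injection-site effects excepted.
- Section 8.5: "Patients removed from study for unacceptable adverse events will be followed until resolution or stabilization of the adverse event", directly after a general 20-year follow-up statement.
- Section 13.4, for patients who discontinue: "If they agree to receive communication from us, we will follow-up with them 30 days following administration of the IP".

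**The concern.** PFS needs two things from every patient: progression status, and the last date on which that status was known. Section 11.0 asks for neither after discontinuation. Section 14.0 then lets the clock run to the end of follow-up without saying which follow-up is meant. A patient known to be alive, but whose disease status nobody has recorded, can stay in the risk set as progression-free. Death does not correct this, because the same sentence lists death as a censoring date.

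The effect would be a PFS curve that is too high, and a descriptive comparison of FES uptake with progression that mixes observed progression-free time with unobserved time. Discontinuation is also not limited to tracer reactions. Section 11.0 requires it when a patient enters a trial of another investigational agent, and Sections 3.2 and 17.0 recruit from other studies. A change of treatment at progression could be the very moment at which progression data cease.

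**Working it through.** **What the plan's own figures cover.** The plan states no PFS median, event count, discontinuation rate or PFS power, so there is no PFS figure to reproduce. Its only power calculation (Section 17.0) concerns percent change in FES SUV. With power = Φ(δ√n/SD − z) and n = 20:
- δ = 40 − 20 = 20, SD 25, one-sided 0.05: 0.973 (stated 0.97).
- δ = 35 − 20 = 15, SD 25, one-sided 0.05: 0.850 (stated 0.85).
- δ = 20, SD 25, two-sided 0.05: 0.947 (stated 0.95).
- δ = 20, SD 30, two-sided 0.05: 0.846 (stated 0.85).

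All four reproduce, and none uses progression follow-up.

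**The sections side by side, for a patient who withdraws consent but permits survival data.** Section 11.0 keeps survival contact. Sections 8.1 and 17.0 foresee progression data for patients in general, but this patient was asked only about survival. Section 14.0 sets the censoring date at termination of follow-up. If that means survival follow-up, the time between the last progression assessment and the last survival contact counts as progression-free. If it means progression follow-up, it does not. The text does not choose.

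**Size, near worst case (assumed figures).** Take 20 patients and exponential PFS with true median 6 months. Suppose k patients never have a progression recorded and are carried past the median. The expected Kaplan-Meier median t solves

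(20 − k)·S0(t) + k = 10, so S0(t) = (10 − k)/(20 − k) and t = 6·log2[(20 − k)/(10 − k)].

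- k = 2: 6·log2(18/8) = 7.0 months (+17%).
- k = 3: 6·log2(17/7) = 7.7 months (+28%).
- k = 4: 6·log2(16/6) = 8.5 months (+42%).

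**Size, milder case (assumed figures).** A simulation of 400,000 exponential PFS times assumed that progression data stop at month 3 for a share d of patients, that stopping is unrelated to prognosis, and that earlier progressions are recorded. Survival contact continues with a median of 36 months after the later of progression or month 3, capped at 60 months. Censoring at last survival contact gives these Kaplan-Meier medians in months:

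| True median | d = 5% | d = 10% | d = 20% | d = 30% |
|---|---|---|---|---|
| 6 | 6.2 | 6.4 | 7.0 | 7.7 |
| 12 | 12.7 | 13.4 | 15.2 | 17.8 |
| 18 | 19.0 | 20.3 | 23.3 | 27.9 |

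Censoring the same patients at the last progression assessment returns the true median within 0.1 month in every cell. Under these assumptions, the whole overstatement comes from the choice of censoring date.

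**The case against.** A reader might infer that patients who stop are followed for survival only and that PFS is therefore certainly biased. The documents do not support that. Section 11.0 names survival but does not exclude progression, and it leaves room for other data a withdrawing patient allows. Sections 8.1 and 17.0 provide for progression follow-up with no exception, and Section 6.1 secures access to records. The treatment being stopped in Section 11.0 is study imaging, since Section 8.0 gives nothing to treat the cancer, and stopping imaging does not by itself end chart follow-up. The censoring sentence can also be read as progression follow-up, in which case no unobserved time is counted.

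Nor would the unclear rules produce differences between sites: Section 2.2 describes a single-site study. Sections 8.5 and 13.4 are largely safety follow-up and not competing PFS rules. The sharper tension is between Section 4.1, which ends involvement, and Section 11.0, which continues it.

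PFS is also secondary. Associations with progression may be examined descriptively in about 20 patients, and no test or decision depends on them.

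These points stand, and they limit the concern to a risk. They do not remove it. The favourable readings have to be assembled from other sections, the section that governs discontinuation and withdrawal omits the endpoint's key variable, and no wording fixes the censoring date.

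**Conclusion.** The point holds as an unspecified rule that could bias PFS upward. The documents do not show that a miscount will occur. The exposure is clearest for a patient who withdraws consent but permits survival data.

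For an assumed true median of 6 months, the overstatement is about 0.4 to 1.0 month at 10 to 20% discontinuation with progression data ending at month 3. It is about 1.0 to 2.5 months in the near worst case with the same share (2 to 4 of 20 patients). It is essentially nil if censoring is at the last progression assessment and stopping is unrelated to prognosis. Every rate and median here is assumed.

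The primary SUV analysis and its power do not depend on this. It is a cheap improvement to a descriptive secondary endpoint.

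**What to change.** 1. In Section 11.0, state that progression and survival both continue to be collected from clinical records after discontinuation, and on withdrawal of consent seek permission for both. Section 6.1 already obtains agreement to record access at entry.
2. In Section 14.0, censor patients without recorded progression at the last date on which progression status was assessed.
3. Reconcile Sections 4.1, 8.1 (Treatment Plan Overview), 8.5, 11.0 and 13.4 on which follow-up applies after discontinuation, and cross-refer them. How that is settled is for the sponsor and the investigator.

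The first change matters even with the second in place. If patients stop because their disease is progressing, earlier censoring removes the unobserved time but does not recover the missing event.

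The cost is protocol wording and some chart abstraction. The small downside is that some patients are censored earlier, so nominal follow-up is shorter.
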